Finally, IRRs have been hypothesized to be a reaction by autoantibodies to the treatment drug or possibly from the release of cytokines from CD20 expressing cells as they are destroyed by ocrelizumab causing a “cytokine storm”. Understanding this process may lead to mechanisms that may aid in ameliorating these infusion reactions. If they are associated with ADA, then it might be possible to predictively premedicate these patients only. Alternatively, if they are associated with cytokine release, it may be possible to eliminate premedication in patients who are already CD20⁺ cell depleted in subsequent infusions. Therefore, we will assay the profile of certain cytokines in the serum 4 hours after start of ocrelizumab infusion.

Since ocrelizumab has entered the market, third party payers within and outside the US have required that the FDA or EMA approved versions of anti-CD20 monoclonal antibodies be used in the treatment of MS, namely ocrelizumab. Currently, we estimate several thousand MS patients in the US and Sweden are taking rituximab currently. Thus, it will be important to demonstrate that switching from a chimeric anti-CD20 to a more fully humanized anti-CD20 does not lead to unexpected infusion reactions and does not increase the probability of development of anti-drug antibodies.

The Rocky Mountain MS Center (RMMSC) at the University of Colorado Anschutz Medical Campus prescribed rituximab infusions for 533 MS patients in the last 12 months, of which 323 patients received their infusion at the University of Colorado Hospital's Outpatient Infusion Center between September, 2015-March, 2016. The RMMSC is one of the few sites nationwide with large numbers of MS patients treated with rituximab. On March 28, 2017, Ocrevus (ocrelizumab) was approved by the FDA for the treatment of primary progressive and relapsing multiple sclerosis. With the approval of ocrelizumab, current rituximab users are being counselled by their MS providers at RMMSC to consider switching to ocrelizumab if it is the only anti-CD20 MAB covered by their insurance.

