Standard of care rituximab doses are 1000 mg given as first dose followed by 500mg (or 1000 mg if evidence of early B cell recovery) every 6 months thereafter. However, [The B cell depletion with rituximab can last up to two years in some patients with good efficacy demonstrated after a single dose in the HERMES study for up to a year.³](#) Patients are often out of window due to difficulties in obtaining insurance approval within the 6 month time window. Therefore, we will include those patients that receive rituximab infusions within a 12 month window.

Although ocrelizumab may be administered on an outpatient basis, patients may be hospitalized for observation at the discretion of the investigator. Ocrelizumab infusions should always be administered in a hospital or clinic environment under close supervision of the investigator or a medically qualified staff member. Each ocrelizumab infusion should be given as a slow IV infusion over approximately 150 minutes (2.5 hours) for the 300-mg dose. To reduce potential Infusion Related Reactions (IRRs), all patients will receive prophylactic treatment with 100 mg of methylprednisolone (or equivalent IV steroid), administered by slow IV infusion, to be completed approximately 30 minutes before the start of each ocrelizumab infusion.

It is also strongly recommended that the infusion is accompanied by prophylactic treatment with an analgesic/antipyretic such as acetaminophen/paracetamol (1 g) and/or an IV or oral antihistamine (such as IV diphenhydramine 50 mg or equivalent dose of alternative) 30 – 60 minutes prior to the start of an infusion to reduce potential IRRs. Patients administered a sedating antihistamine for the treatment or prevention of IRRs should be given appropriate warnings concerning drowsiness and potential impairment of ability to drive or operate machinery.

Since transient hypotension may occur during ocrelizumab infusion, the investigator may wish to withhold anti-hypertensive medications 12 hours prior to ocrelizumab infusion.

Ocrelizumab must not be administered as an IV push or bolus. Well-adjusted infusion pumps should be used to control the infusion rate, and ocrelizumab should be infused through a dedicated line. It is important not to use evacuated glass containers (to prepare the infusion), which require vented administration sets, because this causes foaming as air bubbles pass through the solution.

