4.5.1 Assessments during Treatment

The following evaluations will be conducted during and post treatment:

Study Visits and Procedures Summary:

Study visits for the switching group include a) screening visit, b) first infusion of 300 mg of ocrelizumab (day 1 or T₀), c) 300 mg of ocrelizumab infusion on day 15 (T₁), d) 600 mg of ocrelizumab at 6 months (+/- 2 weeks) after day 1 (T₂) and, e) a research termination visit between month 12 and 18 - (+/- 2 weeks)(T₃). In some cases, screening procedures may be performed on the first infusion day rather than as a separate visit. The patient may continue on 600 mg of ocrelizumab or (if the patient prefers) 500mg rituximab at T₃, or 12 to 18 months after Day 1 (T₀). A month is defined as 28 days. Study visits for the comparator group include only standard of care infusion of rituximab, up to two infusions per patient, approximately 6 months apart. Research data on IRRs for the comparator group will be collected from the medical records.

A summary of all procedures for switching group is outlined under “Schedule of Events” in **Table 1** below. During the screening visit, patients will be consented for the study and receive both a medical and full neurological exam. Verification of their hepatitis B and C status including testing will be conducted if a patient has not been tested in the last two years. MS disease history and demographic information will also be collected. Patients will also receive an EDSS exam and take an online version of the PDDS (done as standard of care- on an iPad).

The Expanded Disability Status Scale (EDSS) is a commonly used assessment that allows clinicians to objectively measure changes in the disability status of MS patients using unbiased clinical raters.⁷ The **EDSS** provides a total score on a scale that ranges from 0 to 10. The first levels 1.0 to 4.5 refer to people with a high degree of ambulatory ability and the subsequent levels 5.0 to 9.5 refer to the loss of ambulatory ability. The range of main categories include (0) = *normal neurologic exam*; to (5) = *ambulatory without aid or rest for 200 meters; disability severe enough to impair full daily activities*; to (10) = *death due to MS*. In addition, it also provides seven subscale measurements called Functional System (FS) scores.

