monitored through standard of care assessments for this population to include a complete metabolic panel (CMP) and complete blood counts (CBC) with differential. Second, their immune profile will be evaluated through an immunoglobulin panel and analyzing T and B cell subsets using flow cytometry by the clinical laboratories at the University of Colorado Hospital. Samples for the cytokine analysis will be drawn on a similar schedule. For the cytokine analysis, blood samples will be collected prior to and after each infusion in CPT tubes. Because moderate to severe infusions reactions can delay infusions, we will plan to add an additional blood draw when these reactions are detected to keep timing of the blood draws more consistent and to capture any possible peak in cytokine levels during these reactions should they be occurring. Plasma will be derived by centrifuging at 1500g for 15 min and then will be aliquoted and stored at -80C. Cells will be reconstituted in freezing media (20% fetal bovine serum, 10% DMSO) and stored at -80C for further analysis. Additionally, plasma samples will be analyzed by MesoScale SECTOR Imager 2400 for evaluation of cytokine levels. Blood draws for the anti-drug antibody analysis will also be drawn at T₁ and sent to PPD Laboratories, Richmond, VA using cryopreserved blood samples as a single batch at the end of the study and analyzed for cytokine analysis.

Patients will receive 100 mg of methylprednisolone 30 minutes before administration of ocrelizumab at each infusion cycle (T₀-T₂). Following the infusion, nursing staff will record IRR using the National Cancer Institute's Common Terminology for Adverse Events Scale. Patient self-assessment of IRRs will also be captured. Adverse events will also be recorded as described in Section 5 by either the nursing staff or study coordinators. Finally, at the last research termination visit (T₃), only blood samples, AEs and concomitant medications will be collected from study patients. Concomitant medications include those used for the treatment for spasticity, depression, or fatigue and other prescription and non-prescription concomitant treatments that will be captured from the patient directly.

Patients will then receive ocrelizumab or rituximab, if they wish, as ongoing therapy. Ocrelizumab and infusion costs will be provided by Genentech until ocrelizumab is approved by the FDA and available to the patient through their insurance plan.

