4.9.6 Determination of Sample Size

The sample size will be a convenience sample. It is anticipated a minimum of 100 patients will qualify for each cohort (200 total) resulting in studying 300 infusions with ocrelizumab and 200 infusions with rituximab. This is an observational study not designed to demonstrate superiority of ocrelizumab over rituximab in efficacy but instead indicate the magnitude of the relative tolerability and immunogenicity. The primary endpoint is the difference in the percentage of IRRs between the two study groups. In addition, both study groups will include treatment experienced patients on rituximab who have experienced a minimum of two infusions and either continue to stay on rituximab or switch to ocrelizumab.

To estimate study power with the proposed sample size of 100 infusions in each group, we conducted a chart review of 50 patients at the Rocky Mountain MS Center who are currently taking rituximab and examined their IRRs using the proposed IRR grading scale (see section 3.3.1) from Grade 0-5. The number and severity of IRRs were captured following their third rituximab infusion. The highest grade of an IRR that occurred during the infusion was recorded. Our pilot data revealed that following the third rituximab infusion, 14.3% of patients had an IRR of which 85.71% were Grade 0, 12.24% were grade 2 and 2.05% were Grade 3. Hauser et al., found that following the second infusion of rituximab in patients, the majority of whom (60%) were not taking a DMT for 6 months prior to initiating rituximab only 20.3% experienced in an IRR.³

Using IRR estimates from our pilot data and establishing a clinically meaningful difference of 20% increase in IRRs, we conducted the following power analysis for a sample of 95 patients (assuming a 5% attrition rate after recruiting 100 patients in each study group). An IRR proportion for ocrelizumab users at 34.3% compared with 14.3% for rituximab (obtained from our pilot data) for a two sided (alpha = 0.05) two sample proportion test for the null hypothesis of no difference between rituximab and ocrelizumab in proportion of IRRs would result in 90% power for 95 patients per group.

In response to the FDA IND letter, “the power analysis in Section 4.9.6 of the protocol appears to compare the infusion-related reaction (IRR) rate at the third rituximab infusion (14.3%) to that of the first infusion of OCR (34.3%). Because

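### Steroid premedication meant to reduce the primary endpoint is mandated before ocrelizumab, but premedication, dose and B-cell status are not listed for collection on comparator infusions, so the planned analysis cannot tell a drug difference from a co-treatment difference

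*Combined protocol and SAP*

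**What the plan says.** **Ocrelizumab infusions.** Section 4.3.1 states that "all patients will receive prophylactic treatment with 100 mg of methylprednisolone (or equivalent IV steroid), administered by slow IV infusion", and the rest of that sentence ties this to each ocrelizumab infusion. Sections 4.4 and 4.5.1 and Table 1 repeat it, always for ocrelizumab or the switching group. An analgesic/antipyretic and/or an antihistamine is strongly recommended but not required.

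**Rituximab infusions.** These are standard of care, "1000 mg given as first dose followed by 500mg (or 1000 mg if evidence of early B cell recovery) every 6 months thereafter". No section states what premedication accompanies them.

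**Comparator data.** "Research data on IRRs for the comparator group will be collected from the medical records", according to section 4.5.1, and section 4.5.2 says the same of follow-up. Section 5.1 adds clinical relapses and serious adverse events. Sections 4.2, 4.5.1 and 4.9.2 add demographic, disease and disability variables. Infused dose, premedication and B-cell results are not listed. Table 1 covers the switching group only, and section 2.2 limits the B-cell objective to that group.

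**Adjustment.** Section 4.2 names age, disease duration and EDSS as examples of covariates. Section 4.9.4 says that if matching balances the demographic and disease variables (with PDDS in place of EDSS), confounding is settled and unadjusted tests suffice.

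**The concern.** The co-treatment is given to prevent the event that the primary endpoint counts. It is mandated in one group and undocumented in the other. Matching on age and gender, and balance on disease history, say nothing about what was given on the day of infusion, so the rule in section 4.9.4 could declare the groups comparable without looking at this factor.

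B-cell status raises a related question. The Introduction suggests that IRRs may come from cytokines released as CD20-expressing cells are destroyed. On that hypothesis a patient whose B cells have recovered may be at higher risk, and early recovery is also what leads to the higher rituximab dose. Comparator dose is therefore a marker of a status that the plan itself links to the outcome.

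At stake is the reading of the main result. The study is meant to show whether switching brings unexpected infusion reactions. A difference, or the absence of one, could arise from the drug or from the co-treatment, and the listed data would not show which.

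**Working it through.** **1. The plan's own figure.** Section 4.9.6 takes 34.3% against 14.3%, two-sided alpha 0.05, and says this "would result in 90% power for 95 patients per group". With mean proportion 0.243:

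- SE under the null = √(2 × 0.243 × 0.757 / 95) = 0.0622
- SE under the alternative = √((0.143 × 0.857 + 0.343 × 0.657) / 95) = 0.0605
- z = (0.200 − 1.96 × 0.0622) / 0.0605 = 1.29, so power = 90.1%

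The stated 90% reproduces. Recruiting 100 with 5% attrition gives 100 × 0.95 = 95.

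**2. What is not given.** Two quantities are needed and the documents supply neither. They are assumed here:

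- RR, the risk ratio of steroid premedication on IRR: 0.5 to 1.0
- f, the share of comparator infusions given steroid: 0 to 100%

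Ocrelizumab is fixed at 100% steroid by protocol.

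**3. Reading A: 34.3% and 14.3% are the rates under equal premedication.** The observed comparator rate is 14.3% × (f + (1 − f)/RR).

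| RR | f | Comparator rate | Difference seen | Power, 95 per group |
|---|---|---|---|---|
| 0.8 | 0 | 17.9% | 16.4 points | 74% |
| 0.7 | 0 | 20.4% | 13.9 points | 57% |
| 0.5 | 0 | 28.6% | 5.7 points | 13% |
| 0.8 | 50% | 16.1% | 18.2 points | 83% |
| 0.7 | 50% | 17.4% | 16.9 points | 76% |
| 0.5 | 50% | 21.4% | 12.9 points | 51% |
| any | 100% | 14.3% | 20.0 points | 90% |

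If the drugs do not differ under equal premedication (both 14.3%) and f = 0, the comparator rate is 14.3%/RR. The chance of a significant result favouring ocrelizumab is then about 10% (RR 0.8), 20% (RR 0.7) or 67% (RR 0.5).

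**4. Reading B: 14.3% already reflects local practice.** The pilot rate comes from charts of 50 patients at the centre with no stated restriction on premedication, so this reading is equally possible. Power for the observed contrast is then unchanged and only its meaning shifts. The rituximab rate if every infusion had steroid would be 14.3% × RR / (f × RR + 1 − f). With f = 0:

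- RR 0.8: 11.4%, so a 20-point observed difference would be 22.9 points like for like
- RR 0.7: 10.0%, 24.3 points
- RR 0.5: 7.15%, 27.15 points

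**5. What separates these cases.** Only f and its companions for antihistamine and antipyretic do so, and none is among the comparator data listed. All the figures in steps 3 and 4 are illustrations; none is an estimate of bias in this study.

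**The case against.** The strongest reply is that the study compares switching with continuing rituximab as routine care. Dosing by B-cell recovery is part of that routine, so a regimen contrast answers much of the stated question. This stands in part: it is why the primary contrast should stay as planned and why rituximab dose is not simply a confounder. It does not support reading the result as a property of the drug.

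Other replies also have force. The comparator charts come from the same infusion centre and may well contain dose and premedication. The covariate list in section 4.2 is open-ended. Section 4.2 already warns that interpretation is limited, although its stated ground is different collection of IRRs and not co-treatment.

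Four stronger readings are tempting and are not supported:

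- **That comparators go without steroid.** The plan is silent on rituximab premedication, and silence is not evidence of imbalance. If routine care gives the same premedication, this part of the problem disappears.
- **That a dose-mix bias can be computed.** A reader might assign 14.3% to 500 mg infusions and a higher rate to 1000 mg infusions, and call the excess bias. The pilot charts were not restricted by dose, so 14.3% already contains whatever mix was in use and any dose effect would be counted twice.
- **That switchers' steroid use rests on patient report.** Section 4.5.1 says that "Concomitant medications include those used for the treatment for spasticity, depression, or fatigue" and other treatments, taken from the patient directly. Table 1, however, has a separate methylprednisolone row at T0, T1 and T2. Only the optional antihistamine and antipyretic lack a row.
- **That the Introduction's premedication question needs comparator data.** The idea that "it might be possible to predictively premedicate these patients only" concerns anti-drug antibodies, which with cytokines are measured only in switchers.

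**Conclusion.** The point holds as a gap in planned data and analysis, and not as a demonstrated bias. The mandate for a co-treatment aimed at the primary endpoint applies to one group, the matching fields are not listed for the other, and section 4.9.4 would treat demographic and disease balance as enough.

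The size cannot be determined from the documents. Over the assumed ranges (RR 0.5 to 1.0, f 0 to 100%), the distortion of a 20-point difference runs from zero to 14.3 points under reading A (20.0 − 5.7) and from zero to 7.15 points under reading B. In both, less steroid among comparators favours ocrelizumab. Heavier antihistamine, antipyretic or steroid use among comparators would act the other way and is not modelled.

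The gap is closable if the charts hold the data. One limit remains: if steroid were given before all infusions in one group and none in the other, recording it would expose the problem but adjustment could not remove it.

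**What to change.** 1. For each analysed infusion in both groups, abstract from the infusion-centre record the dose given, the steroid, antihistamine and antipyretic given (drug and dose), and the latest CD19/CD20 result where available. Specify these fields before abstraction starts, above all for the retrospective infusions after August 1, 2016.
2. Tabulate them by group and infusion.
3. Keep the primary contrast as planned. Add one sensitivity analysis, adjusted for premedication or restricted to infusions with comparable premedication, where the groups overlap.
4. Apply any breakdown by B-cell status to both groups. Show rituximab dose descriptively only: splitting comparators alone by dose would set mostly depleted comparators against switchers of mixed B-cell status.
5. If premedication does not overlap, report the result as a comparison of whole regimens.
6. Amend section 4.9.4 so that balance on demographic and disease variables is not by itself taken to rule out confounding.

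The cost is a few more fields from charts already being opened for IRRs, one table and one sensitivity analysis. The drawbacks are some missing fields for retrospective infusions and smaller strata. No change to care is proposed; the request is to record what is given.

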4.3.2 Dosage Modification

Dose modification of ocrelizumab is not permitted.

4.3.3 Overdosage

There is no experience with overdosage in human clinical trials.

4.4 Concomitant and Excluded Therapy

e.g., Infusion protocol concomitant therapy: all patients will receive prophylactic treatment with 100 mg of methylprednisolone (or equivalent IV steroid), administered by slow IV infusion, to be completed approximately 30 minutes before the start of each ocrelizumab infusion

Excluded medications are any significantly immunosuppressive medications or treatments (i.e., radiation therapy) as determined by the treating neurologist.

4.5 Study Assessments

Full protocol review and approval will be obtained from the University of Colorado's IRB board, known as the Colorado Multiple Institutional Review Board (COMIRB) including a scientific review from COMIRB's Scientific Advisory and Research Committee. Signed, IRB-approved informed consent will be obtained from patients prior to any assessments.

4.5.1 Assessments during Treatment

The following evaluations will be conducted during and post treatment:

Study Visits and Procedures Summary:

Study visits for the switching group include a) screening visit, b) first infusion of 300 mg of ocrelizumab (day 1 or T₀), c) 300 mg of ocrelizumab infusion on day 15 (T₁), d) 600 mg of ocrelizumab at 6 months (+/- 2 weeks) after day 1 (T₂) and, e) a research termination visit between month 12 and 18 - (+/- 2 weeks)(T₃). In some cases, screening procedures may be performed on the first infusion day rather than as a separate visit. The patient may continue on 600 mg of ocrelizumab or (if the patient prefers) 500mg rituximab at T₃, or 12 to 18 months after Day 1 (T₀). A month is defined as 28 days. Study visits for the comparator group include only standard of care infusion of rituximab, up to two infusions per patient, approximately 6 months apart. Research data on IRRs for the comparator group will be collected from the medical records.

A summary of all procedures for switching group is outlined under “Schedule of Events” in **Table 1** below. During the screening visit, patients will be consented for the study and receive both a medical and full neurological exam. Verification of their hepatitis B and C status including testing will be conducted if a patient has not been tested in the last two years. MS disease history and demographic information will also be collected. Patients will also receive an EDSS exam and take an online version of the PDDS (done as standard of care- on an iPad).

The Expanded Disability Status Scale (EDSS) is a commonly used assessment that allows clinicians to objectively measure changes in the disability status of MS patients using unbiased clinical raters.⁷ The **EDSS** provides a total score on a scale that ranges from 0 to 10. The first levels 1.0 to 4.5 refer to people with a high degree of ambulatory ability and the subsequent levels 5.0 to 9.5 refer to the loss of ambulatory ability. The range of main categories include (0) = *normal neurologic exam*; to (5) = *ambulatory without aid or rest for 200 meters; disability severe enough to impair full daily activities*; to (10) = *death due to MS*. In addition, it also provides seven subscale measurements called Functional System (FS) scores.

The Patient-Determined Disease Steps (PDDS) is a PRO version of the clinician-reported EDSS which hones the stages of cane use and thus is more responsive to mid-range disability changes.⁸ This tool asks the patient to characterize level of disability into one of nine steps (0=normal, 1=mild disability, 2=moderate disability, 3=gait disability, 4=early cane, 5=late cane, 6=bilateral support, 7=wheelchair scooter, 8=bedridden). The PDDS will be used to characterize (and to control for) disability in both study groups at all study time points.

Following the screening visit, patients in the switching group will be scheduled for their first infusion of ocrelizumab at their next regularly scheduled infusion date (no more than six months after their last rituximab infusion). Study infusion cycle T₁ will have an acceptable window of +/- 4 days since it is given 15 days apart, while infusion cycles T₂ and T₃ will have an acceptable window of +/- 14 days since it is administered 6 months later.

Prior to the start of the infusion, blood samples will be collected that will be utilized for several purposes. At infusion cycle time points, T₀, T₂ and T₃ blood samples for the following assessments will be drawn. First, patients will be

monitored through standard of care assessments for this population to include a complete metabolic panel (CMP) and complete blood counts (CBC) with differential. Second, their immune profile will be evaluated through an immunoglobulin panel and analyzing T and B cell subsets using flow cytometry by the clinical laboratories at the University of Colorado Hospital. Samples for the cytokine analysis will be drawn on a similar schedule. For the cytokine analysis, blood samples will be collected prior to and after each infusion in CPT tubes. Because moderate to severe infusions reactions can delay infusions, we will plan to add an additional blood draw when these reactions are detected to keep timing of the blood draws more consistent and to capture any possible peak in cytokine levels during these reactions should they be occurring. Plasma will be derived by centrifuging at 1500g for 15 min and then will be aliquoted and stored at -80C. Cells will be reconstituted in freezing media (20% fetal bovine serum, 10% DMSO) and stored at -80C for further analysis. Additionally, plasma samples will be analyzed by MesoScale SECTOR Imager 2400 for evaluation of cytokine levels. Blood draws for the anti-drug antibody analysis will also be drawn at T₁ and sent to PPD Laboratories, Richmond, VA using cryopreserved blood samples as a single batch at the end of the study and analyzed for cytokine analysis.

Patients will receive 100 mg of methylprednisolone 30 minutes before administration of ocrelizumab at each infusion cycle (T₀-T₂). Following the infusion, nursing staff will record IRR using the National Cancer Institute's Common Terminology for Adverse Events Scale. Patient self-assessment of IRRs will also be captured. Adverse events will also be recorded as described in Section 5 by either the nursing staff or study coordinators. Finally, at the last research termination visit (T₃), only blood samples, AEs and concomitant medications will be collected from study patients. Concomitant medications include those used for the treatment for spasticity, depression, or fatigue and other prescription and non-prescription concomitant treatments that will be captured from the patient directly.

Patients will then receive ocrelizumab or rituximab, if they wish, as ongoing therapy. Ocrelizumab and infusion costs will be provided by Genentech until ocrelizumab is approved by the FDA and available to the patient through their insurance plan.

For the comparator group, they may be approached to gauge interest in the study via telephone. If they are interested, the consent can be sent to them. These patients will be given the following options: 1) complete consent process orally over the phone with coordinator (and a treating physician if patient desires), sign and date the consent form and send back to coordinator via mail, fax, or email, 2) complete consent process with coordinator (and a treating physician if patient desires) in person at their next scheduled rituximab infusion. In either case, data collection will not begin until written consent is obtained. Following each rituximab infusion, nursing staff will record IRR using scales as part of standard care.

As required by the University of Colorado's Institutional Review Board, an independent Data and Safety Monitoring Board (DSMB) will meet at initiation of the study and every 6 months thereafter until the end of the study.

Table 1. Schedule of Events (for switching group)

Data Collection Event	Screening Visit^a	Day 1 (T₀) 300 mg of OCR^a	Day 15 (T₁) 300 mg of OCR)	6 months (T₂) (600 mg of OCR)	12 -18 months research termination visit (T₃)
Informed Consent	X				
Medical Exam	X				
Physical Exam	X				
Demographics and MS Disease History	X				
Concomitant Meds	X	X	X	X	X*
Vital Signs		X	X	X	X
Hepatitis B and C evaluation confirmed	X				
EDSS	X				
PDDS	X				X*
Pre-infusion blood draw:					
Lab: CBC, CMP		X		X	X
Lab: B and T cell subsets by flow cytometry		X		X	X
Lab: immunoglobulin panel		X		X	X
Lab: Binding antibodies		X		X	X
Pre and post-infusion blood draw and during moderate/severe reactions:					
Lab: Cytokine levels		X	X	X	
Administration of Ocrelizumab		X	X	X	
Pre-medication of 100 mg of methylprednisolone		X	X	X	
Nurses record IRRs		X	X	X	
Nurses/Study Coordinator record AE		X	X	X	X*
Patient self-report of IRRs		X	X	X	

* may be completed over the phone

